### **Inclusion criteria**

The study will include adult patients with ASA physical status 1–3, requiring surgery for an ENT pathology and having a presumed difficult airway which will be divided in two groups: anatomically difficult airway group according to The Simplified Airway Risk Index Scale(SARI), with a SARI score  $\geq 5$ , and patients with obstructing airway pathology: oropharyngeal tumors, cervical masses, previous neck surgery or radiotherapy, also with predicted difficult intubation forming group 2.

The two groups are needed because ENT pathology is generating a particular challenge in airway approach which is different from the rest of the pathology and the main goal is to show the efficiency of Rigid Tube for Laryngoscopy (RTL) versus gold standard in intubating patients with various types of airway issues. We decided to include at least ten patients in each group, a reasonable number for testing a new method of airway control. Signed informed consent was obtained from all patients explaining the procedure in simple words and detailing the risks and the safety measures.

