### **Exclusion criteria**

Stridor or marked laryngeal or tracheal stenosis, vocal cords polyps, emergency surgery, high aspiration risk, decompensated cardiac and pulmonary disease, very poor dentition and patient refusal were criteria of exclusion from the study. We've also decided to reject from the study patients who exhibit a Cormack-Lehane grade 1 glottis view when conventional laryngoscopy is performed. In case of difficult mask ventilation causing marked desaturation, requiring prompt action to secure the airway, we will take the first chance to secure the airway considering potentially unsafe the use of the experimental RTL. The

investigator underwent a training period before starting the study, consisting in ten direct laryngoscopies with the RTL under an ENT specialist guidance to get used to manoeuvring the RTL and acquire a reasonable level of skill in using it.

A pre-anaesthetic exam was performed with careful assessment of the airway. Patients with features predictive for difficult intubation gathering at least 4 points on the SARI score and with no known airway pathology were included in group 1. Patients from the group 2, with obstructing airway pathology had a perioperative endoscopic examination of the airway with a flexible rhino-laryngoscope which is meant to evaluate the distorted anatomy and exclude glottic or subglottic stenosis which could contraindicate blind intubation over an intubating tube introducer (gum elastic bougie).

Premedication consisted of 1 or 2 mg of Midazolam given intravenously 15 minutes before the intervention, in the preoperative room. Standard hemodynamic and respiratory monitoring were applied: ECG, non-invasive arterial blood pressure, oxygen saturation, respiratory frequency, end-tidal CO2. Difficult airway kit was prepared. The RTL was in position with the light source attached. Patients were pre oxygenated for 5 minutes and induction of anesthesia with propofol- succinylcholine and fentanyl was performed. After 1 minute of mask ventilation, we noted the oxygen saturation on the pulse oximeter, classical laryngoscopy was performed with a McIntosh curved blade laryngoscope, and CormackLehane glottis visualization was registered- possible values: 1,2,3,3.5,4.

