The RTL intubation starts with the head in extension and in sniffing position, using a retromolar approach, with teeth protection. The approaching side was chosen based on patient pathology and it could be changed during the procedure if the investigator considered so. We used a 1.2-2.2 cm wide and 15-30 cm long tube depending on patient preoperative assessment and pathology. During advancement of the RTL, the investigator is careful to apply the minimum of pressure so the oro-pharyngeal tissue and dentition should not be injured. The RTL was advanced slowly until it reached the epiglottis, then the

epiglottis was lifted, and the vocal cords visualised. The thyroid cartilage was a land point when advancing the RTL, keeping the RTL on its direction and holding pressure on it and thus adjusting the larynx position so the epiglottis and glottis should be easier to visualise with the RTL. After a proper alignment between the RTL and the glottis was achieved, the bougie was introduced through the RTL into the glottis, the RTL extracted, and the standard cuffed intubating tube with lubricated tip was placed in the trachea gently, over the bougie. Secretions were aspirated through the RTL as needed. If the glottis is visualised during the RTL advancement, it will be withdrawing slowly, and the larynx will be manipulated with the left hand from the thyroid cartilage until the glottis comes into sight. A second attempt will be started advancing slower, heading to the thyroid cartilage while looking for epiglottis. Once epiglottis is lifted the RTL must be directed as anteriorly as possible, returning to the epiglottis and starting new lifting if not successful. We decided to stop the attempt at 120 s or if the patient desaturated to 80%.

We note the Cormack-Lehane glottis visualization at classical laryngoscopy- with values ranging from 1 to 4, the time from classical laryngoscopy until the airway was secured in seconds, the lowest oxygen saturation during the procedure and any other complications occurring during procedure. we document every patient data regarding airway, ENT pathology and difficult airway history. We recorded images to document the challenging cases and prove the efficiency of the RTL. We also took notice of any complications that may have arisen during or after the procedure.

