### **Statistical analysis plan**

The statistical part will consist of creating a table with the pre-anaesthetic and demographic variables – mean and standard deviation. The results will be included in a table and graphic image and the data which will be analysed are:

- time for conventional laryngoscopy and for intubation with the RTL- mean and SD
- grade of glottis view as from Cormack-Lehane scale- median and full range

- haemoglobin oxygen saturation during the procedure with the lowest noted as mean and SD
- complications during and after the procedure

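### The only planned result that names both techniques sets the time of a conventional look beside the time of a complete RTL intubation, and the single recorded interval cannot yield the two times separately

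*Combined protocol and SAP*

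**What the plan says.** The goal, under Inclusion criteria, is comparative and concerns intubation: "the main goal is to show the efficiency of Rigid Tube for Laryngoscopy (RTL) versus gold standard in intubating patients".

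The two techniques are described in the procedure text that follows the Exclusion criteria heading. For the conventional blade: "classical laryngoscopy was performed with a McIntosh curved blade laryngoscope, and CormackLehane glottis visualization was registered". No bougie or tube passage by that route is described. For the RTL, once the glottis is aligned: "the bougie was introduced through the RTL into the glottis, the RTL extracted, and the standard cuffed intubating tube with lubricated tip was placed".

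One time is listed for recording: "the time from classical laryngoscopy until the airway was secured in seconds".

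The Statistical analysis plan then has a single time item: "time for conventional laryngoscopy and for intubation with the RTL- mean and SD". It plans no difference, test or interval.

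**The concern.** The time item names a laryngoscopy for one device and an intubation for the other. If the text is followed, the first clock covers a graded look and the second covers a look plus everything needed to place the tube. Exact timing of both would not cure this, because the mismatch lies in what is timed.

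It matters because nothing else in the analysis list can carry the comparative goal. The Cormack-Lehane grade is noted for the conventional blade only ("We note the Cormack-Lehane glottis visualization at classical laryngoscopy"). Saturation and complications are taken over the whole procedure ("the lowest oxygen saturation during the procedure and any other complications occurring during procedure"). The two patient groups are airway types, not techniques, so there is no separate conventionally intubated group to supply a comparator. A reader looking for the answer to RTL versus gold standard will find only the two time means, and they do not say whether the RTL reaches a glottic view sooner or later than the blade.

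**Working it through.** **Plan's own figure.** There is none to reproduce. The documents give no expected time, SD or margin for either technique. The sample size ("We decided to include at least ten patients in each group") comes with no calculation and does not bear on this point.

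**Steps side by side.**

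| Step | Conventional blade | RTL |
|---|---|---|
| Insert device and obtain view | described | described |
| Grade the view | described | not listed |
| Pass bougie | not described | described |
| Remove device, place tube | not described | described |

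**Definitions, per patient.**
- L: time of the conventional look
- V: RTL time from insertion to glottic view
- T: time for bougie passage, RTL removal and tube placement

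**What the time item reports, read as two times.** Mean(L) and mean(V + T). The gap between them is

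mean(V + T) − mean(L) = mean(V − L) + mean(T).

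The first term is the like-for-like contrast. The second is positive in every completed RTL intubation and has nothing to offset it on the conventional side. If the devices give a view equally fast, V = L and the whole gap is mean(T). More patients estimate mean(T) more precisely but do not remove it.

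**How large.** The documents give no value for L, V or T. Two sets of purely assumed times show how little can be said:
- L = 15 s, V = 90 s, T = 20 s: gap = 90 + 20 − 15 = 95 s, of which T is 20/95 = 21%.
- L = 15 s, V = 15 s, T = 20 s: gap = 15 + 20 − 15 = 20 s, of which T is 20/20 = 100%.

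The share due to the unmatched steps could lie anywhere over a wide range, so no percentage is claimed.

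**Whether the data can supply the item.** The one listed interval starts with the conventional blade and ends at the secured airway. It equals L + V + T plus any time between the two devices. One total cannot be split into L and V + T. The recording text and the analysis item therefore do not fit together.

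**The other reading.** If the time item means that single combined interval, the recording text and the analysis item agree. But then no planned result distinguishes the techniques, and the comparative goal has no analysis at all.

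**The case against.** **The plan is descriptive.** It schedules means and SDs, and the item itself labels one quantity laryngoscopy and the other intubation. Two correctly labelled descriptive times are not in themselves an error. This stands as far as it goes: the plan contains no formal biased test. But the means are to be tabulated and graphed in a study whose stated goal is comparative, and no other item names both techniques.

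**The look-only reading is inferred.** No start or stop point is given for either time, and the documents do not expressly rule out a conventional tube attempt. That is true. The inference rests on the steps described, and none of them is a conventional intubation.

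**The plan must make the RTL look slower.** A reader might infer this, but the documents do not support it. What is certain is that T is added to the RTL side. The sign of the total depends on V − L, which is unknown: if the RTL reached a view sooner than the blade by more than T, its mean would still be the shorter.

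**The plan throws away paired information.** This too is tempting. Each patient does have both looks, but an RTL view time is not recorded, so no existing paired look-time difference is being discarded. With complete pairs, the mean within-patient difference also equals the difference of the means; pairing changes only the spread and the interval.

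**A matched time to view is not a clean comparison either.** The conventional look always comes first, patients with a grade 1 conventional view are excluded, and the devices may reach different grades. Nor does time to view answer a question about intubation. All of this stands. It limits what the replacement result can claim and is why the fix keeps that result descriptive.

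**Conclusion.** The point holds as a mismatch of tasks in the one analysis item that names both techniques, together with a recorded interval that cannot produce the two times. The mismatch adds mean(T), a positive quantity of unknown size, to the RTL side of any side-by-side reading. This assumes that the time item means two times and that the conventional step ends at grading, as the procedure text describes. If the item instead means one combined time, the mismatch disappears but so does any two-technique result. On either reading the text needs changing.

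The documents do not support going further: neither a stated share of the gap nor a conclusion that the RTL will necessarily appear slower. This is a change that should be made. It costs little and alters what the trial can conclude.

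**What to change.** **Recording text (procedure section).** Replace the single interval with marked times: insertion of each device, the graded glottic view with each device, and the secured airway, with each event defined. Record the view grade for the RTL as well as for the conventional blade.

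**Time item (Statistical analysis plan).** Replace it with two results:
1. Time from insertion to graded glottic view for each device, summarised as a descriptive within-patient difference with a 95% CI. Give the grade reached with each device and the number of patients with no view beside it. State that the order was fixed with the conventional look first, and that grade 1 conventional views were excluded.
2. RTL time to secured airway, reported alone, labelled as having no conventional comparator and not contrasted with the conventional look time.

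**Cost.** Five time marks per patient where one interval is now listed (two for each device, plus the secured airway), one additional view grade, and a reworded analysis item. The burden is more events to note during a busy procedure. The change does not alter how patients are managed.

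### Mean and SD alone cannot show how low saturation fell or how many reached the 80% stop, and RTL time has no rule for patients not intubated with the RTL

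*Combined protocol and SAP*

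**What the plan says.** The Statistical analysis plan section is descriptive. For saturation it lists "haemoglobin oxygen saturation during the procedure with the lowest noted as mean and SD", and for time "time for conventional laryngoscopy and for intubation with the RTL- mean and SD". Only the glottic grade gets a different summary: "grade of glottis view as from Cormack-Lehane scale- median and full range". There is also a line for complications, without definition or statistic, and a table and a graphic whose content is not described.

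The procedure text, which follows under the Exclusion criteria heading, sets the limits: "We decided to stop the attempt at 120 s or if the patient desaturated to 80" (per cent). A further attempt is foreseen: "A second attempt will be started advancing slower, heading to the thyroid cartilage while looking for epiglottis". The recorded items include "the time from classical laryngoscopy until the airway was secured in seconds" and "the lowest oxygen saturation during the procedure and any other complications occurring during procedure". RTL success, number of attempts and reason for stopping are not among them.

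The Inclusion criteria section sets the size: "We decided to include at least ten patients in each group, a reasonable number for testing a new method of airway control".

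**The concern.** The plan is purely descriptive, so the choice of summary is the whole analysis. Two things readers will want to know about a new airway device are how far saturation fell, including how many patients reached the protocol's own limit, and how often the device did not achieve intubation. A mean and SD from about ten values, bounded above at 100% and possibly including one or two low ones, answers neither.

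Time has a further gap. It ends when the airway is secured. A patient whose airway was not secured with the RTL has no completed RTL time, and a time that ended by another route is not an RTL time. The plan does not say whether such patients are left out, entered at a limit or entered at the total elapsed time. The mean RTL time depends on that unstated choice, and leaving them out makes the device look faster.

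**Working it through.** The plan gives no power calculation or expected values, so it has no figure of its own to reproduce. The check uses n = 10 per group (the stated minimum), the 80% and 120 s limits, and the 100% ceiling, which follows from the unit. **All patient values below are assumed, for illustration.** SD = √[Σ(x − mean)² / (n − 1)].

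**1. Lowest saturation: two different groups, one summary**
- Set A, nine at 98 and one at 80: mean = (882 + 80)/10 = 96.2. Sum of squares = 9 × 1.8² + 16.2² = 29.16 + 262.44 = 291.60. SD = √(291.60/9) = 5.69.
- Set B, 88, 88, 88, 98 and six at 100: mean = (264 + 98 + 600)/10 = 96.2. Sum of squares = 3 × 8.2² + 1.8² + 6 × 3.8² = 201.72 + 3.24 + 86.64 = 291.60. SD = 5.69.
- In A one patient is at the stop limit. In B none is, but three are at 88%. Median and range separate them: 98 (80 to 98) against 100 (88 to 100).
- In A the single patient at 80% supplies 262.44/291.60 = 90% of the sum of squares. Mean + 1 SD is 96.2 + 5.69 = 101.9%, above the ceiling, so the pair cannot be read as a typical spread around the mean.

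**2. RTL time: dependence on the unstated rule**

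Assume eight intubated patients at 25, 28, 30, 32, 35, 38, 42 and 50 s (sum 280), and two not intubated with the RTL.
- Two dropped: 280/8 = 35.0 s, SD = √(466/7) = 8.2.
- Two entered at 120 s: (280 + 240)/10 = 52.0 s, SD = √(12026/9) = 36.6.
- Two entered at 240 s, as if two full attempts were used: (280 + 480)/10 = 76.0 s, SD = √(67706/9) = 86.7.
- Median of all ten with the two ranked slowest: (35 + 38)/2 = 36.5 s under either code.

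**3. How likely is at least one such patient?**

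P(at least one in ten) = 1 − (1 − p)¹⁰. For an assumed true rate of reaching a stop of 5%, 10% or 20% this is 40%, 65% or 89%.

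**4. What the counts would say**

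Exact (Clopper-Pearson) two-sided 95% intervals with n = 10:
- 0/10: 0 to 30.8%
- 1/10: 0.3% to 44.5%
- 2/10: 2.5% to 55.6%

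The intervals are wide, which is itself information that a mean and SD would not convey.

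**The case against.** Mean and SD are legitimate descriptive statistics for bounded or skewed data. The plan fits no normal curve and makes no test, so a mean plus SD above 100% asserts nothing about any patient. The documents hold no saturation or time data, so the shape of either distribution is assumed. Desaturation might appear under complications, and the graphic might show individual values. The median used for glottic grade proves little, because that scale is ordinal. All of this is fair, and it limits the point to what the summaries leave out. It does not remove it: the complications line is undefined, the procedure text names lowest saturation apart from other complications, and nothing says that the graphic shows individual patients.

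Some stronger readings are tempting but not supported:
- *That the 80% limit truncates the saturation data.* It triggers a stop and is not a floor. The recorded lowest value can fall below 80%.
- *That recorded time is capped at 120 s, or that every stopped attempt is a failure.* The limit applies to one attempt and another is foreseen. Recorded time starts at classical laryngoscopy, so it can exceed 120 s. Entering patients at 120 s is only one possible coding.
- *That everything needed is already recorded.* RTL success and stop reason are not listed. A lowest value of 80% or below points to a saturation stop, but a time stop cannot be derived from total time.
- *That the plan sets out to conceal failures.* Nothing in the text suggests intent.

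**Conclusion.** The point holds as a reporting weakness with a cheap remedy. No stated figure is wrong and no clinical limit is in question. At the stated minimum of ten per group, mean and SD cannot distinguish a group in which a patient reached 80% from one in which nobody did; sets A and B agree exactly on both. The mean RTL time is not defined until the plan says what happens to patients not intubated with the RTL. In the assumed example it moves from 35 s to 52 s, or to 76 s under a third coding, while the median with those patients ranked slowest stays at 36.5 s.

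The sizes rest on invented patient values and will differ in the real data. The conclusion itself rests only on the stated summaries, the group size, the two stop limits, the 100% ceiling and the absence of a rule. A larger group would weaken the influence of single patients but would not supply the missing counts or the missing rule.

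**What to change.** In the Statistical analysis plan section:
- Report lowest saturation and time by group as median and full range, with quartiles if wanted. Mean and SD may stay alongside for comparison with other reports. If a mean RTL time is shown, state how many patients it covers.
- Report the number and percentage whose lowest saturation was 80% or below, with an exact 95% confidence interval. This uses the protocol's existing limit as a reporting cut and changes nothing in management.
- Report the number and percentage not intubated with the RTL, with an exact 95% confidence interval, and state the denominator.
- In the median for RTL time, rank patients not intubated with the RTL as slowest instead of dropping them. The upper end of the range is then given as not intubated. If half or more are not intubated, state that the median was not reached.

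In the list of recorded items, add one simple field for RTL success and reason for stopping.

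The cost is a few lines of text, a slightly longer table and that one field. No extra patients or procedures are needed.
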